267 unable to activate the smartphone application associated with the blood pressure monitor, they may  
268 submit their blood pressure readings by taking a time-stamped photo of the blood pressure monitor  
269 display. Blood pressure will be calculated as the average of two measurements that are taken five minutes  
270 apart, which is in accordance with previous literature (14). Once their blood pressure readings have been  
271 confirmed as being elevated, patients will undergo randomization in a 1:1 ratio to intervention or control  
272 using simple randomization through a random number generated at the time of study enrollment.

273

274 ***Informed Consent***

275 Informed consent will be attained from subjects prior to enrollment using an eConsent process.  
276 Patients will be told that a study is being conducted for evaluation of blood pressure, and focused on  
277 strategies to optimize treatment using technology. They will also be informed of how their personal  
278 information will be secured and that all analysis will be conducted on de-identified data. Because  
279 Medisafe is a free application and notification may lead to use of this technology in the control arm,  
280 patients will not be told about Medisafe before randomization. After randomization patients in the  
281 intervention arm will be provided with information and instructions to download Medisafe. During the  
282 informed consent process, there will be a contact form as well as a phone number and email available to  
283 patients for any questions or to withdraw from the study.

284

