#### 285 ***Study Procedures***

286 Prior to randomization, patients will be asked to complete a baseline assessment. This will  
287 consist of baseline demographics including cardiovascular comorbidities, use of cigarettes, and education  
288 level (15). The Morisky 8-item adherence scale will also be collected, which has been validated to  
289 accurately capture anti-hypertensive medication adherence by self-report (8). Baseline hypertension  
290 knowledge will also be assessed in accordance with Oliveira et. al (16). Subjects will also be asked to  
291 complete the Consumer Health Activation Index (CHAI) as a marker for patient activation, as developed  
292 by Wolf et al. Blood pressure monitors will then be mailed after the patients complete the baseline  
293 assessment.

294 Patients assigned to the intervention arm will be emailed with instructions to download the  
295 Medisafe application. Through an integration with Medisafe, Evidation Health will confirm that the  
296 application has been downloaded and launched at least once within two days from randomization.  
297 Patients who do not download and launch the application at least once within two days will be contacted  
298 by email two more times and provided the instructions for download until they launch the application. If

299 they still do not launch the application, they will be contacted twice via telephone, then one final time by  
300 email. If after three reminder e-mails and two phone calls the participant still does not launch the  
301 application, they will not be contacted further about downloading the application, but they will remain in  
302 the intent-to-treat analysis group.

303 Patients assigned to the control arm will not receive any intervention.

304 At two time points, four and eight weeks after randomization, all subjects assigned to intervention  
305 and control will be e-mailed and asked to measure their blood pressure using the Bluetooth-enabled blood  
306 pressure cuff and its associated smartphone application (all blood pressures will be done via two  
307 measurements, taken at least five minutes apart, and averaged (7)). If there is no blood pressure  
308 measurement received within 2 days after the intended upload date, there will be two reminder e-mails  
309 sent until a blood pressure measurement is received. If there is still no blood pressure measurement  

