387 correlations between repeated blood pressure readings for any individual subjects. If there are additional  
388 blood pressure readings from patients who took their blood pressure more often than required, the  
389 longitudinal models will be re-run to include these additional values.

390 In subgroup analyses, we will evaluate whether the impact of Medisafe differed for subjects who  
391 interacted with Medisafe frequently (defined as being in the upper median of use for the Medisafe  
392 application based on number of days logged in during the study period) as compared to subjects who  
393 interacted with Medisafe less frequently. We will perform this analysis by including categorical variables  
394 for high and low use in our outcome model, whereby control subjects are indicating by null values for

395 both indicators. We will also evaluate effect modification by hypertension knowledge (16) recorded at  
396 baseline.

397

398 ***Sample Size***

399 With a change in blood pressure of 5mmHg, which has previously been shown to be clinically  
400 significant (12,13), a standard deviation of 16.7mmHg, a power of 80%, and an alpha of 0.05 there would  
401 need to be 312 patients enrolled. With allowance for 20% loss to follow-up, the study will seek to enroll  
402 390 patients total to have an 80% power with an alpha of 5%. With a standard deviation of 1.6 (8) and a  
403 sample size of 390 patients, we will be able to detect a 0.5 Morisky score difference between the groups  
404 with a power of 87%.

405

406 ***Risks Associated with the Intervention***

407 Since the intervention under investigation is not aimed at altering a patient's treatment, but rather  
408 to promote adherence to treatments that they have already been prescribed, the risk will be minimal.  
409 There is a possible risk of patients receiving escalating anti-hypertensive medications from their treatment  
410 team due to non-adherence, and with the better adherence through Medisafe reminders there could be  
411 medication induced hypotension. During the informed consent process and on the blood pressure  
412 measurement guidance sheet there will be recommendations to reach out to their treatment team if they  
413 ever have a blood pressure > 180/120 mmHg or < 90/50 mmHg. The informed consent will also clearly  
414 state that no component of the study, including the home blood pressure cuff use and study personnel, is a  

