458 clinically significant (12,13), a standard deviation of 17.6mmHg, a power of 80%, and an alpha of 0.05  
459 there would need to be 312 patients enrolled. With allowance for 20% loss to follow-up, the study will  
460 seek to enroll 390 patients total to have an 80% power with an alpha of 5%. With a standard deviation of  
461 1.6 (8) and a sample size of 390 patients, we will be able to detect a 0.5 Morisky score difference between  
462 the groups with a power of 87%.

463

464 Final analytic plan

465 *Analytic Plan*

466 The Center for Healthcare Delivery Science (C4HDS) at Brigham Women's Hospital will  
467 conduct all analysis on de-identified data. Analyses will be performed by an intent-to-treat basis, where  
468 subjects will be analyzed in the groups they are assigned to during randomization.

469 We will begin by comparing the baseline patient characteristics in each of the arms using t-tests,  
470 chi-square tests or their non-parametric analogues, as appropriate. We will evaluate for rates of missing  
471 data between the two study arms to ensure that it is non-differential.

472 We will use linear regression to assess the impact of Medisafe on the study's 2 primary outcomes  
473 (change in blood pressure and self-reported adherence) between the two study groups. Our null  
474 hypothesis will be that there is no difference in the change in blood pressure between the two groups after  
475 12 weeks.

476 Our primary models will adjust for unbalanced covariates between the two groups (i.e. age,  
477 gender, ethnicity, BMI, comorbidities, number of antihypertensive medications, total number of  
478 medications, education, exercise level, cell phone use) should any exist using a p-value threshold of 0.05  
479 and will impute missing outcome data where 12 week outcome data is unavailable. Imputation will be  
480 performed using the PROC MI command in SAS and will include the covariates defined above as well as  
481 intermediate outcomes (i.e. blood pressure at weeks 4 and 8). Multiple imputation with 5 imputations  
482 will be used and the imputed values will be inspected to ensure in-range values. After imputation,  
483 analyses will be conducted on the imputed data set and the results will be combined using the standard  
484 rules from Rubin et al. In sensitivity analyses, we will analyze only those subjects for whom we have  
485 complete outcome data (i.e. a complete case analysis).

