486 In secondary analyses, we will determine the number of patients that had their hypertension  
487 controlled (i.e., <140/90mmHg) during the study period in both arms, and calculate an odds ratio using

488 multivariate logistic regression with covariates indicated above. In supplemental analyses, we will repeat  
489 our analyses with longitudinal modeling methods that incorporate blood pressure readings at 4, 8, and 12  
490 weeks after randomization. This will be done using generalized estimating equations to account for  
491 correlations between repeated blood pressure readings for any individual subjects. If there are additional  
492 blood pressure readings from patients who took their blood pressure more often than required, the  
493 longitudinal models will be re-run to include these additional values.

494 In subgroup analyses, we will evaluate whether the impact of Medisafe differed for subjects who  
495 interacted with Medisafe frequently (defined as being in the upper median of use for the Medisafe  
496 application based on number of days logged in during the study period) as compared to subjects who  
497 interacted with Medisafe less frequently. We will perform this analysis by including categorical variables  
498 for high and low use in our outcome model, whereby control subjects are indicating by null values for  
499 both indicators. We will also evaluate effect modification by hypertension knowledge (16) recorded at  
500 baseline.

501

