#### 502 *Sample Size*

503 With a change in blood pressure of 5mmHg, which has previously been shown to be clinically  
504 significant (12,13), a standard deviation of 17.6mmHg, a power of 80%, and an alpha of 0.05 there would  
505 need to be 312 patients enrolled. With allowance for 20% loss to follow-up, the study will seek to enroll  
506 390 patients total to have an 80% power with an alpha of 5%. With a standard deviation of 1.6 (8) and a  
507 sample size of 390 patients, we will be able to detect a 0.5 Morisky score difference between the groups  
508 with a power of 87%.

509

510 Summary of changes to analytic plan

511 More concrete analysis methods for evaluating baseline patient characteristics as well as a list of  
512 potentially unmatched covariates are now provided which was not included in the original plan. Missing  
513 12-week outcome data is also addressed in the final plan, specifically performing multiple imputation via  
514 the PROC MI function in SAS.

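### The high-use versus low-use analysis splits only the app arm on log-in days counted after randomisation, so it mixes selection with effect and cannot show whether the app's impact differed

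*Supplement*

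**What the plan says.** The analysis appears in the final protocol (Analytic Plan) and in the same words in the final analytic plan (Analytic Plan). It begins "In subgroup analyses, we will evaluate whether the impact of Medisafe differed for subjects who" and then defines the frequent group: "interacted with Medisafe frequently (defined as being in the upper median of use for the Medisafe", continuing "application based on number of days logged in during the study period) as compared to subjects who" used it less. The model is specified through indicators: "for high and low use in our outcome model, whereby control subjects are indicating by null values for" both of them. Controls are therefore the common reference for the high-use and low-use halves.

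Three other parts of the plan bear on this:

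- **Adjustment.** "Our primary models will adjust for unbalanced covariates between the two groups (i.e. age" and further listed items), and only where the arms differ at p < 0.05. The baseline Morisky score and the activation index, both collected before randomisation (final protocol, Study Procedures), are not on the list.
- **Non-launchers.** After the reminders are exhausted, "application, they will not be contacted further about downloading the application, but they will remain in" the intent-to-treat group.
- **A neighbouring analysis.** The next sentence of the plan examines effect modification by baseline hypertension knowledge. That variable is measured before randomisation in both arms. Nothing in the text separates the status of the two analyses.

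**The concern.** Log-in days arise after randomisation and can be observed only in patients given the app. Patients who log in often may also be those who take their tablets and follow study instructions more reliably. Those who never launch the app have no log-in days and would presumably fall in the low-use half. The controls are an unselected mix of patients who would have been high users and patients who would have been low users. Each app-arm half is thus a self-selected group set against an unselected one, and the contrast estimates selection plus effect. Adjusting for covariates that differ between the arms does not address differences between high and low users.

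The plan nevertheless words the result as a difference in the app's impact. If the main effect is null or small, a reader could take this analysis as evidence that the app works in those who use it, and the design would not support that.

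**Working it through.** **Inputs from the documents.** Allocation is 1:1 (final protocol, Subject Recruitment and Randomization) and planned enrolment is 390, so 195 per arm, or 156 per arm after 20% loss. The target is 5 mmHg. The SD is 16.7 mmHg in the final protocol (Sample Size) and 17.6 mmHg in the final analytic plan (Sample Size). Both values are carried below. For adherence, the target is 0.5 Morisky points and the SD is 1.6.

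**Assumptions.** The true app effect is zero. Use has correlation r with the outcome within the app arm for reasons other than the app. Use and outcome are treated as jointly normal, and the stated SDs as the SDs of the analysed outcomes. The documents give no value for r, so a range is shown.

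**Check on the plan's own figure.** The plan gives no figure for the use analysis. Its Morisky power checks the sample size and the two-sided 5% convention. The standard error is 1.6 × √(2/195) = 0.162. Then 0.5/0.162 − 1.96 = 1.13, which gives power of 87%, as stated.

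**Bias under no effect.** The mean of the upper half of a standard normal variable is √(2/π) = 0.798. Each half therefore differs from controls by 0.798 × r × SD, in opposite directions, and high minus low is 1.596 × r × SD.

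| r | Gap, SD 16.7 (mmHg) | Gap, SD 17.6 (mmHg) | Each half vs controls, SD 17.6 (mmHg) | Gap, Morisky (points) |
|---|---|---|---|---|
| 0 | 0 | 0 | 0 | 0 |
| 0.1 | 2.7 | 2.8 | 1.4 | 0.26 |
| 0.2 | 5.3 | 5.6 | 2.8 | 0.51 |
| 0.3 | 8.0 | 8.4 | 4.2 | 0.77 |

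The correlation at which the spurious gap equals the target is 5/(1.596 × 17.6) = 0.18 or 5/(1.596 × 16.7) = 0.19 for blood pressure. For Morisky it is 0.5/(1.596 × 1.6) = 0.20.

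**Chance of a significant high-low difference under no effect.** The planned three-group model was simulated with 8,000 replicates per setting. With SD 17.6 and 195 per arm, p < 0.05 occurred in 5% of trials at r = 0, 20% at r = 0.1, 62% at r = 0.2 and 92% at r = 0.3. With 156 per arm the figures were 5%, 17%, 52% and 86%. For Morisky at r = 0.2 they were 60% with 195 per arm and 51% with 156.

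A hand check at r = 0.2 with halves of 97 and 98: the standard error is 17.6 × √(1/97 + 1/98) = 2.52. Then 5.62/2.52 − 1.96 = 0.27, or about 61%.

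The comparison of the whole arms stayed at zero, apart from simulation error, in every setting.

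**The case against.** A reader might infer that this analysis is bound to show a difference even if the app does nothing. The documents do not support that. A false difference needs an association between log-in days and outcome that does not run through the app. The documents report none, and at r = 0 the test keeps its 5% level.

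The case is also weaker for blood pressure than for adherence. The blood pressure endpoint is a change from randomisation. A stable trait such as conscientiousness affects both baseline and week 12, so much of its influence would cancel. A correlation with change needs something more, such as a trend related to the trait or a stronger reaction to being in a study. Adherence is not written as a change score, its baseline value is not among the listed covariates, and it is self-reported. An association with engagement is therefore easier to believe there.

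The consequence is limited too. The analysis comes after the primary, secondary and supplemental analyses and is labelled a subgroup analysis. The primary analysis keeps everyone in the assigned arm. A claim that the app works in those who use it is a risk in later reporting; the plan does not make that claim.

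All of this stands, and it limits the size and certainty of the bias. It does not rescue the interpretation: whatever r is, comparing self-selected halves with all controls does not identify a difference in the app's effect, and nothing elsewhere in the plan corrects for it.

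**Conclusion.** The point holds as a fault of interpretation in a lower-tier analysis. The use split is a non-randomised comparison worded as a difference in the app's impact. It can produce such a difference with no app effect. The gap would be 2.7 to 8.0 mmHg (SD 16.7) or 2.8 to 8.4 mmHg (SD 17.6) for an assumed r of 0.1 to 0.3, and a correlation just under 0.2 is enough to match the 5 mmHg target. For adherence, r = 0.2 matches the 0.5-point target. These sizes rest on the assumed r and on the normal approximation; log-in days with many zeros would change them somewhat.

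It would be wrong to extend this to the main result. The intent-to-treat comparison is not affected.

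**What to change.** 1. Stop describing the contrast as a difference in the app's impact. Keep the use split only as a descriptive comparison, labelled non-randomised.
2. To study effect by engagement, build a prediction of use in the app arm from baseline variables, including the baseline Morisky score and activation index already collected. Apply it to both arms and test the arm-by-predicted-use interaction. Cross-fit the prediction, so that app-arm patients are not scored by a model fitted to their own data.
3. A complier-average effect may be added, with assignment as the instrument and app launch as the exposure. The plan should say that it estimates the effect of launching, not of frequency of use, so it does not replace step 2. It should also state the assumptions: negligible app use among controls, and no effect of assignment except through launch. The first matters because the app is free and the protocol describes launch tracking only for the intervention arm.

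**Cost.** Steps 1 and 2 need revised wording, one prediction model and one interaction test, with no new data. Step 3 needs either the assumption about controls or a question to them about app use.

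The price of step 2 is precision. With both arms cut into halves of about 97.5, the interaction has a standard error of 17.6 × √(4/97.5) = 3.56 mmHg, against 17.6 × √(2/195) = 1.78 mmHg for the main effect. At two-sided 5%, 80% power is reached only for a difference in effect of about (1.96 + 0.84) × 3.56 = 10 mmHg. Imperfect prediction of use would lower the power further. The result should be reported as an estimate with its interval.

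### The imputation model leaves out hypertension knowledge and its product with arm, so the planned effect-modification test is pulled modestly toward zero (minor)

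*Supplement*

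**What the plan says.** The Analytic Plan text is the same in the Final protocol and the Final analytic plan.

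- **Imputation inputs.** Imputation is to be "performed using the PROC MI command in SAS and will include the covariates defined above as well as" the intermediate BP readings. The covariates begin with age and continue: "gender, ethnicity, BMI, comorbidities, number of antihypertensive medications, total number of" "medications, education, exercise level, cell phone use) should any exist using a p-value threshold of 0.05". That makes ten. The intermediate readings and number of imputations are given as "intermediate outcomes (i.e. blood pressure at weeks 4 and 8). Multiple imputation with 5 imputations". Hypertension knowledge, study arm and their product are not mentioned.
- **Data analysed.** After imputation, "analyses will be conducted on the imputed data set and the results will be combined using the standard" combination rules. A sensitivity analysis is limited to participants with "complete outcome data (i.e. a complete case analysis").
- **The test.** Under subgroup analyses: "We will also evaluate effect modification by hypertension knowledge (16) recorded at" baseline. No model form, scale, power or data set is given.
- **Related analysis.** Repeated BP readings are modelled in a supplemental analysis: "weeks after randomization. This will be done using generalized estimating equations to account for" within-person correlation.

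The Study Procedures section of the Final protocol collects hypertension knowledge at baseline. It collects the Morisky score at baseline and week 12 only.

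**The concern.** An imputation model should contain every term that the analysis model will test. If it omits an interaction, missing outcomes are drawn as if that interaction were absent, except for the part that other predictors carry. Mixing those draws with the observed values dilutes the interaction. The variance from Rubin's rules also ends up too large for this term, so the test rejects too seldom.

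The other subgroup analysis, by app use, rests on a variable measured after randomisation. Knowledge is therefore the only pre-specified baseline modifier, and a null finding would in part reflect the imputation.

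Adding arm or the baseline outcome alone would not cure this. Neither carries the arm-by-knowledge relation into the imputed values.

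**Working it through.** **1. Missing share.** The plan needs 312 participants and allows 20% loss: 312 / 0.80 = 390. The expected number missing is 390 - 312 = 78, or 20%. The plan states no power for the interaction, so there is no such figure to reproduce.

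**2. Setting.** From the documents: N = 390, 1:1 allocation, SD 17.6 mmHg (Final analytic plan), main effect 5 mmHg, alpha 0.05 taken as two-sided, 5 imputations. Assumed: knowledge split 50/50, outcomes missing completely at random, true interaction 10 mmHg, arm already in the imputation model.

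- Full data: SE = 4 x 17.6 / √390 = 3.57; 10 / 3.57 = 2.81; power about 80%.
- Complete cases: SE = 4 x 17.6 / √312 = 3.99; 10 / 3.99 = 2.51; power about 71%.

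The Final protocol gives SD 16.7 instead. Full-data power would then be about 84%, and the proportional shrinkage below would not change.

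**3. Expected shrinkage.** Let m be the missing share and c the part of the week-12 interaction that the week-4/8 readings carry. Then shrinkage = m x (1 - c). With a common correlation ρ among the readings, each intermediate reading has coefficient ρ / (1 + ρ). If a fraction f of the effect is already present at weeks 4 and 8, c = f x 2ρ / (1 + ρ).

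- No usable week-4/8 data: c = 0; 0.20 x 1 = 20%.
- ρ = 0.5, f = 1: c = 0.667; 0.20 x 0.333 = 6.7%.
- ρ = 0.5, f = 0.5: c = 0.333; 0.20 x 0.667 = 13.3%.
- ρ = 0.7, f = 1: c = 0.824; 0.20 x 0.176 = 3.5%.

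**4. Simulation (2,000 trials per row, 20% missing).** The estimates agree with step 3.

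| Week-4/8 BP | Estimate as share of truth, terms omitted | Power, omitted | Power, included | Points lost |
|---|---|---|---|---|
| None usable | 80% | 51% | 67% | 16 |
| ρ 0.5, f 1 | 93% | 69% | 71% | 2 |
| ρ 0.5, f 0.5 | 87% | 61% | 70% | 9 |
| ρ 0.7, f 1 | 97% | 75% | 75% | 0 |

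With the terms included, the estimate is about 100% of truth in every row. Complete-case analysis is also unbiased here, with power 69-71%. With no true interaction, the rejection rate is about 2-3% when the terms are omitted and about 5% when they are included.

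Taking knowledge as continuous, with an assumed 5 mmHg per SD, gives 6-14% shrinkage and 3-9 points lost with week-4/8 BP. Without it the figures are 20% and about 17 points.

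**5. Sensitivity.**

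- *Missing share.* With no week-4/8 data, shrinkage is 10%, 20% and 31% at 10%, 20% and 30% missing. At 30% the power loss is 27 points without week-4/8 BP, and between none and 17 points with it.
- *Smaller interaction.* At 5 mmHg with no week-4/8 data, power is 12% omitted, 23% included and 28% had nothing been missing.
- *Arm also omitted, no week-4/8 data.* The estimate is 79% of truth; power is 49% against 66%.

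**6. Morisky.** There is no week-4/8 score, so if BP says little about it, c is near 0. With the plan's SD of 1.6 and an assumed interaction of 0.45 per SD of knowledge, the full-data signal is 0.45 x √390 / (2 x 1.6) = 2.78. That is close to the 2.81 in step 2, so the first row of the table applies approximately. The expected estimate is 0.80 x 0.45 = 0.36.

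**The case against.** **The data set is not named.** The imputation sentences have the primary models as their subject, and the knowledge sentence is silent. This stands as an ambiguity. Still, the general statement that analyses use the imputed data follows directly, and complete-case analysis is assigned only to sensitivity analyses. Imputed data is the natural reading, though not the only one.

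**A safeguard exists.** Complete-case analysis would be unbiased for the interaction if data are missing at random given arm and knowledge. That is correct, but the plan does not assign it to this test.

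**The effect is small and conservative.** This largely stands. A reader might infer that imputed values carry almost none of the arm-by-knowledge relation, so that the test loses much of its power. The plan does not support that for BP: the week-4/8 readings are in the imputation model and carry part of the interaction. The larger loss needs those readings to be absent or uninformative.

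**Sample size is the greater limit.** A 10 mmHg interaction is twice the main effect for which the trial is sized. At 5 mmHg, power is only 28% even with nothing missing. A null result would be weak evidence mainly for that reason.

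**Conclusion.** The point holds as a minor one. If the interaction test uses the imputed data, leaving out knowledge and its product with arm biases the interaction toward zero by at most about the missing share. It also makes the test conservative rather than prone to false claims of effect modification.

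The loss runs from negligible to moderate for BP and is probably at the upper end for Morisky. These sizes rest on the assumed interactions, correlations and missingness completely at random; the documents give none of these. A different loss rate would move the ceiling with it.

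A reader might also infer that this undermines the trial's main result. It does not: this omission concerns one subgroup analysis. Whether leaving arm off the imputation list affects the main comparison is a separate question.

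**What to change.** In the Analytic Plan section of both the Final protocol and the Final analytic plan:

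1. Add baseline hypertension knowledge to the imputation variables for both co-primary outcomes, and run PROC MI separately by randomised arm. Alternatively, include arm, knowledge and their product explicitly.
2. State that the effect-modification test uses these imputed data, and report the complete-case result alongside.

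The cost is one line of text and one of code. Knowledge is already collected at baseline, so no new data are needed.
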